## 7.0 RECORDS TO BE KEPT

- Subject Intake
- Subject Demographics
- Subject Consent Forms
- HIPAA Authorization Form
- Baseline and follow up survey data
- Coded ET use data
- Coded patient health care utilization
- Coded transcripts from interviews with patients

Appendix A  
**CENTER FOR HEALTH ENHANCEMENT SYSTEMS STUDIES**  
**Data and Safety Monitoring Plan**

**Data and Safety Monitoring Committee**

The Center uses the Data Monitoring Committee (DMC) located in the University of Wisconsin's Institute for Clinical and Translational Research (ICTR). The ICTR DMC will provide services to ensure appropriate measures are in place to promote subject safety, research integrity and compliance with federal regulations and local policies. The DMC members will review protocol-specific reports created by statisticians using data pulled from the Research Electronic Data Capture (REDCap) data management tool. These standard reports will include an overview of study objectives, a review of actual and projected accrual rates, an evaluation of patient demographics for balance of randomization, and a summary of the number and seriousness of adverse events. An interim analysis of study results may be performed and source documents may be reviewed to allow the board to independently judge whether the overall integrity and conduct of the protocol remain acceptable based on data provided and reported by the Principal Investigators. The board will make recommendations to the Principal Investigator that could include actions of continuation, modification, suspension, or termination.

In providing oversight for the conduct of this study, the ICTR DMC will meet annually during the 5-year study. Additional meetings may be scheduled as determined by the DMC or as requested by the PIs.

The predefined stopping points for this study will include excess rates of hospital re-admissions or quality of life determinates, exceeding 30% of pre-test values in both cases. We will record events that are deemed to be 'possibly, probably, or definitely' related to the study intervention, and communicate to the AHRQ, DMC and UW IRB in accordance with the following guideline.

What Event is Reported	When is Event Reported	By Whom is Event Reported	To Whom is Event Reported
Fatal or life-threatening unexpected, suspected serious adverse reactions	Within 7 calendar days of initial receipt of information	Investigator	Internal IRBs NHLBI and/or DMC
		Sponsor or designee	FDA (if IND study)
Non-fatal, non-life-threatening unexpected, suspected serious adverse reactions	Within 15 calendar days of initial receipt of information	Investigator	Internal IRBs/ Institutional Officials NHLBI and/or DMC
		Sponsor or designee	FDA All participating investigators
Unanticipated adverse device effects	Within 10 working days of investigator first learning of effect	Investigator	Internal IRBs NHLBI and/or DMC
		Sponsor or designee	FDA (if IDE study)
Unanticipated Problem that is not an SAE	Within 14 days of the investigator becoming aware of the problem	Investigator	Internal IRBs/Institutional Officials, NHLBI and/or DMC
All Unanticipated Problems 	Within 30 days of the IRB's receipt of the report of the UP from the	IRB	OHRP
		Investigator	Internal IRBs and DMC

investigator.		
---------------	--	--

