## 2.0 STUDY OBJECTIVES

**Overview of methods.** We propose a 3-arm RCT to examine whether delivering ET on the smart system (ET- SS) will increase frequency and sustainability of use and improve quality of life, when compared to ET on the laptop (ET-LT). A Control group (ET-C), which will receive no technology (smart system or laptop) or ET, will allow us to assess whether both groups that receive the ET intervention (albeit on different platforms) show equally positive effects relative to control, or whether ET delivered via one platform is more efficacious relative to the control and other intervention group. We will create ET-specific commands so that the smart system operates well with ET (e.g. "Hey Google, I'm ready to take my survey"). The RCT itself will begin by identifying eligible patients and sending them invitation letters from their primary care provider (PCP). Patients who respond will be screened and recruited into the study, baseline data will be collected, and patients will be randomly assigned to a study arm, provided with devices if applicable, and trained. The intervention will last 8 months. Data will be collected at 0, 4, and 8 months. The final months of the study will be spent analyzing and interpreting qualitative and quantitative data and disseminating results through publications, presentations, and real-world field tests.

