### RCT Patient Recruitment

The RCT will involve 291 patients age 60 and older, recruited over 18 months, and randomized into three groups:

1. ET-SS: Patients will receive treatment as usual (TAU) + Smart System + Internet access + ElderTree
2. ET-LT: Patients will receive TAU + laptop + Internet access + ElderTree
3. Control: Patient will receive TAU

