### Patient Consent

Patients must agree to allow monitoring of their ElderTree use and for data to be collected from their EHR (UW Health patients only), as detailed below. The patient will be given the right not to share specific information and will retain the right to revoke their permission at any point.

The consent process will inform potential subjects of:

- (1) the nature and purpose of the study
- (2) the types of data that will be collected from the EHR (by the CHI2 – UW Health patients only)
  - Chronic conditions
  - health care utilization: hospitalizations (admission and discharge), number of ER visits, urgent care visits, PC visits, specialty care visits, long-term care visits, and rehab visits
- (3) the types of data that will be collected from ElderTree
  - Weekly survey data (missed medications, falls, thinking and memory, mood, healthy meals/snacks/drinks, physical activity, quality time with others, sleep, pain, and balance)
  - Use data
- (4) the types of data that will be shared with their primary care physician - a graph that charts weekly scores related to the quality of sleep, nutrition, physical activity, memory, falls, moods, balance, pain, medication adherence and quality time spent with others- for UW Health patients only.
- (5) study risks and measures taken to mitigate
- (6) their right to leave the study at any time
- (7) the timeline of the study

Verbal consent will be documented on the recruitment form and in REDCap and a copy of the IRB-approved consent form will be mailed to participants for their records. All study data outside of REDCap will be stored in a locked cabinet at the Center for Health Enhancement Systems Studies at the UW.

The research team will always have a member available during standard operating hours for participants to contact with questions or issues. If a patient declines to participate, a research team member will determine reasons for non-participation so we can examine how patients who opt out differ from those who choose to participate.

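### Adverse-event recording is conditional on relatedness to the intervention, so the DMC's adverse-event summary has no usable Control comparator

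*Combined protocol and SAP*

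**What the plan says.** The Data and Safety Monitoring Plan (Appendix A) says: "We will record events that are deemed to be 'possibly, probably, or definitely' related to the study intervention". The sentence goes on to say that these events are communicated to AHRQ, the DMC and the UW IRB under the table that follows.

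The DMC's standard reports, built from REDCap, are to include "a summary of the number and seriousness of adverse events". No split by arm is mentioned for that summary.

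The sentence just before the recording rule sets the stopping criteria: "The predefined stopping points for this study will include excess rates of hospital re-admissions or quality of life determinates". The threshold it attaches to these criteria is given as "exceeding 30% of pre-test values in both cases".

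The third arm is defined in section 4.0 (RCT Patient Recruitment) as "Control: Patient will receive TAU", and in section 2.0 as a group "which will receive no technology (smart system or laptop) or ET".

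For UW Health patients, the Patient Consent section lists among the EHR data "health care utilization: hospitalizations (admission and discharge), number of ER visits", with urgent care and other visits.

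In the reporting table, the recipients of most investigator reports are given in the form "Internal IRBs NHLBI and/or DMC".

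**The concern.** One relatedness condition governs both verbs in the Appendix A sentence, recording and communicating. Filtering expedited reports by relatedness is ordinary. Filtering what is recorded is different, because the judgement depends on the arm: an ET participant's event can be attributed to the laptop or smart system, while a Control participant has nothing to attribute it to. The plan does not say who judges relatedness and describes no masking of that judgement.

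The randomised Control group is the natural reference for events that older patients with chronic pain and several other conditions will have anyway. An adverse-event summary without that reference gives the DMC a count it cannot interpret. A few related events in the ET arms say little about whether those arms fare worse than usual care.

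**Working it through.** The plan states no adverse-event rate or safety sample size, so there is no figure of its own to reproduce. The check sets the sections side by side, with one illustrative count.

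**1. Is there another capture rule?** None was found.
- Section 4.0, Unanticipated Events, covers unanticipated problems and refers to Appendix A.
- Table 2 in section 5.0 has no adverse-event measure.
- Section 7.0, Records to be Kept, lists no adverse-event log.
- The Appendix A table sets deadlines and recipients, not what is to be captured.

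Staff following the plan have no instruction to record an event judged unrelated.

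**2. What does the rule yield in Control?** That arm receives treatment as usual, without devices or ElderTree. The expected number of recorded events related to the intervention is therefore 0 by construction.

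**3. Illustrative size.** Inputs: 291 randomised (section 4.0). The allocation ratio is not stated, so 1:1:1 is assumed, giving 291/3 = 97 per arm and 194 in the two ET arms. The 8-month event risk (5%, 10% or 20%, equal in all arms) and the share of ET events judged related (10% to 50%) are also assumptions.
- Control participants with an event, whatever the attribution: 97 × 0.05 = 4.9; 97 × 0.10 = 9.7; 97 × 0.20 = 19.4.
- Both ET arms together: 194 × 0.05 = 9.7; 194 × 0.10 = 19.4; 194 × 0.20 = 38.8.
- Recorded under the rule as written: Control 0; ET arms from 194 × 0.05 × 0.10 = 1.0 to 194 × 0.20 × 0.50 = 19.4.

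With identical true risk in every arm, the adverse-event record would show 0 against anything from about 1 to 19. The ET count would reflect attribution as much as risk.

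**4. Which harm data escape the filter?**

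| Data | Arms covered | Limits |
|---|---|---|
| 30-day readmissions, survey at months 0, 4, 8 | All three | One item; readmissions, not all admissions |
| Falls, survey at months 0, 4, 8 | All three | 6-month recall |
| Quality of life, survey at months 0, 4, 8 | All three | Survey responders |
| EHR hospitalisations, ER and urgent care visits | All three, UW Health patients only | No EHR data for community recruits |
| Deaths | No stated source | Not in the survey or the EHR list in the consent section |

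On falls, a 6-month window at the month-4 survey starts 6 − 4 = 2 months before baseline. At month 8 it starts at month 8 − 6 = 2, so the two windows overlap from month 2 to month 4.

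**5. Does the DMC see these data by arm?** The listed contents of the standard report are objectives, accrual, demographics to check the balance of randomisation, and the adverse-event summary. Readmissions, falls and EHR utilisation are not listed. An interim analysis is optional. The stopping criteria carry no relatedness filter, but their reference is the pre-test value and not Control.

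**6. Recipients.** The governing sentence names AHRQ, the DMC and the UW IRB. The table names NHLBI joined to the DMC by and/or in the rows for serious reactions, device effects and unanticipated problems that are not SAEs. Only the last row names the IRBs and the DMC without that wording. AHRQ, named as sponsor at the front of the document, is not named anywhere in the table. NHLBI is described in section 1.0 as funding another trial by the same team. Read literally, telling NHLBI alone would satisfy the rows for serious reactions as far as the DMC is concerned.

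**The case against.** The best case for the plan has three parts.

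First, the Appendix A sentence does not contain the word only, and it leads straight into a reporting guideline. It may have been meant to define what is recorded for that purpose. The DMC summary speaks of adverse events without qualification, which could mean that wider capture was intended. This stands as a possible intention, but no section carries it out, and a rule that must be guessed will be applied unevenly.

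Second, a reader might infer from the recording rule that harm cannot be compared between arms at all, or that a marked excess of hospitalisations in an ET arm would go unseen. The documents do not support either inference. Section 3.0 says measures are the same in all three arms. Readmissions, falls and quality of life are surveyed three times and entered in REDCap, from which the DMC reports are drawn. Readmission is a secondary outcome analysed by arm. EHR hospitalisations are extracted for UW Health patients. Readmissions and quality of life are themselves stopping criteria, with no attribution required. This part of the objection stands in full and confines the point to the adverse-event summary and to what the DMC is shown.

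Third, this is a behavioural technology trial in which serious harm from the intervention is not the leading worry. That bears on priority, not on whether the wording should be corrected.

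The mismatch of recipients is a separate administrative inconsistency and adds no weight to the main point.

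**Conclusion.** The point holds in a limited form. As written, recording is conditional on relatedness, no other section supplies a capture rule, and Control has no intervention to which an event could be related. The DMC's adverse-event summary therefore has no usable Control comparator. A between-arm comparison of readmissions, falls, quality of life and, for UW Health patients, EHR utilisation remains possible, but the plan does not state that the DMC receives it.

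The size can only be illustrated: roughly 5 to 19 Control participants with an event against a recorded count of 0. This rests on assumed risks of 5% to 20% and assumed equal allocation. The zero does not depend on those assumptions. It depends on reading the recording sentence literally.

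This is worth correcting as a cheap improvement. It does not threaten the primary analysis.

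**What to change.** Three changes to Appendix A:

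1. Replace the recording sentence with something like: *Adverse events that come to the study's attention will be recorded in all three arms, whatever their judged relation to the study intervention. Relatedness will be recorded as an attribute of each event and will be used as a filter only for expedited reporting.*
2. Add to the DMC report a table by randomised arm of data already collected: survey readmissions and falls in all arms; EHR hospitalisations and ER visits for UW Health patients, with their own denominators; and any deaths learned of in follow-up contacts, such as the calls already planned when a survey is not returned within 2 weeks.
3. Reconcile the recipients in the reporting table with the governing sentence, including whether AHRQ or NHLBI is meant and whether notice to the DMC is required or optional.

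The cost is a simple event log and slightly longer DMC reports. The table should carry two cautions. Deaths and hospitalisations of community recruits will be less completely captured. The fall item at month 4 reaches back before baseline and overlaps the month-8 window, so the two counts should not be added. Both limits apply to every arm, so the by-arm table remains useful despite them.

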## **Data Security and Privacy Monitoring Plan**

In accordance with the Health Insurance Portability and Accountability Act (HIPAA), CHESS has adopted the following Data Security and Privacy Monitoring Plan.

### **I. Appointment of Center Data Security Officers.**

- A. [name] and [name] are the security officers for the Center.
- B. Responsibilities of the security officers include:
  - Developing information technology (IT) security policies
  - Increasing security awareness and providing training for all Center faculty and Team Members
  - Providing virus protection for IT resources
  - Maintaining security patches on computing equipment
  - Developing and implementing back up procedures
  - Performing periodic vulnerability scanning on computers
  - Reviewing and updating firewall strategies and policies
  - Enhancing the physical security of IT resources
  - Performing annual review of staff policies and procedures contained in this document
  - Conducting formal HIPAA Risk Assessment Inventory per requirements of the UW HIPAA Office; last review completed summer 2018.

### **II. Policy for Orientation and Training**

- A. All Center students, faculty, and staff are required to complete the UW-Madison **2019-20 HIPAA Privacy & Security Training** course online which is offered in Canvas at <https://canvas.wisc.edu/courses/173269>. Contact [name] if you do not have the HIPAA training on your Canvas dashboard. Please email [name] when you have completed the training. You will need to retake this course annually.
- B. All Center students, faculty, and staff that are involved in human subjects research are required to complete the UW-Madison CITI Human Subjects training online at <https://my.gradsch.wisc.edu/citi/index.php>. Register with your NetID. Select the training for the **UW Social & Behavioral Course**. Please email [name] when you have completed the training. You will need to take a refresher course every three years.
- C. All Center students, faculty, and staff that are involved in human subjects research are required to complete the UW-Madison CITI Human Subjects training online at <https://my.gradsch.wisc.edu/citi/index.php>. Register with your NetID. Select the training for the **GCP—Social and Behavioral Research Best Practices for Clinical Research**. Please email [name] when you have completed the training. You will need to take a refresher course every three years.
- D. Successful completion of the CITI and HIPAA training is required before any team member is allowed access to Protected Health Information (PHI) or Research Data.
- E. All Center Team Members are required to complete training with [name] on Center security procedures and policies.
- F. Sign (on the last page) the “Center Data Security Policy and Privacy Monitoring Plan” upon completion of this training and return to [name].

### **III. Workstation Policy**

- A. All workstations will require login with a unique user name and password.

- B. All workstations are required to be joined to the ENGR domain under the control of the College of Engineering. Access to specific folders on the Center network will be approved by the Center Management team or the study Project Director.
- C. All workstations are required to use anti-virus software that can be remotely administered from the College of Engineering domain.
- D. Users will log-out from or lock workstations when leaving them unattended.
- E. Screen savers will be configured to require a password and to activate after ten minutes of workstation inactivity.
- F. Users requiring remote access to the Center network will only do so with computers specifically certified by a Center Data Security Officer.
- G. Study coordinators or support personnel using desktops in private or public areas must have screens adjusted so that visitors cannot read the screen upon entering the space in case PHI or other confidential information is displayed.
- H. Access to the network or center work stations along with any on-line systems will be terminated immediately following an employee's last day of work at the Center.

#### **IV. Password Policy**

- A. Users will require a password to access any computer connecting to the Center network.
- B. Passwords must meet the requirements of the Computer Aided Engineering department (CAE). CAE password construction help can be found here:  
<https://kb.wisc.edu/cae/page.php?id=8143>.
- C. Ideally the best practice is to re-set your password on a semi-annual basis.
- D. Passwords may not be stored in proximity to the workstation and may not be shared by others.

#### **V. Policy for the Use of Email**

- A. Patient Identifiable, Confidential, or Personnel Data may only be included in an encrypted attachment and should never be sent in the body or subject line of an email message.
- B. Team Members who need to send encrypted attachments should contact a Center Data Security Officer to schedule a training session.

#### **VI. Policy for Storage, Retrieval, and Disposal of Protected Information**

- A. Effective 1/1/14 any new studies must use the REDCap environment for study participant information. Contact [name] for start-up and access information.
- B. Any Patient Identifiable, Confidential, or Personnel Data in electronic form will be stored on secure servers only and **may not** be stored on individual workstations, laptops, or any other endpoint devices. Currently, the only place such information can be stored is the R: Drive for studies prior to 1/1/14 or REDCap.
- C. Study coordinators will have printers in their office for printing any materials that include PHI and/or names of study participants.
- D. All paper-based files will be stored in locked rooms inside locked file cabinets with limited access.
- E. Any offices that contain PHI must be locked when leaving a room.
- F. Servers containing Patient Identifiable, Confidential or Personnel Data must be located within physically secured server rooms which can only be accessed by authorized personnel.
- G. The Center Data Security Officers will be responsible for assigning and restricting access to shared resources on Center servers.
- H. Patient Identifiable, Confidential, and Personnel Data as a general rule may not be copied to or stored on the Center's publicly accessible servers at any time. However, in some studies, patient's name, disease state, and physician are stored within Center applications only accessible via a

secure connection using a codename/password.

- I. Remote access to files on secure Center servers will be provided in a very limited case only through a connection from a certified Center Workstation (see Center Workstation policy above for details).
- J. Storage media containing Patient Identifiable, Confidential or Personnel Data will be rendered unusable before disposal.
- K. All back up media will be stored in locked rooms with limited access.

**VII. Policy for the Use of Endpoints (e.g. Workstation Smartphone, Laptop, Thumb Drive, External Hard Drive) Accessing Patient Identifiable, Confidential, and Personnel Data**

- A. Staff are not allowed to access or store any PHI data on any endpoint unless the endpoint is provided by a Center Data Security Officer ensuring that the endpoint is protected and secured. In addition, any PHI data residing on an endpoint must also be encrypted with the oversight of a Center Data Security Officer.
- B. All endpoints accessing PHI must be owned and provisioned by the Center.
- C. Patient Identifiable, Confidential, and Personnel Data files may not be transported from the Center unless the device/medium is monitored for physical security at all times and the data is encrypted on the mobile device.
- D. Remote access to PHI data must be conducted using a secure encrypted end-to-end connection implementing modern security best practices either over HTTPS or using the WiscVPN connection.

